12.6.2 Evaluation of response

Subjects who complete ¹⁷⁷Lu-J591 + ¹⁷⁷Lu-PSMA-617 treatment combination (2 doses of each investigational agent) and at least 12 weeks of subsequent follow-up evaluations (as described in the Schedule Calendar-Section 6.1) will be considered evaluable (consistent with PCWG3 guidelines). As the timing of response is not known, should the anticipated time to response be determined to be earlier than with other therapies using alternative markers of response, we may not replace subjects who are not evaluable through week 12 on study.

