
We will enroll up to 27 subjects in the Phase II trial utilizing a Simon two-stage design (including the 3-6 patients used for establishing the MTD). For the phase II portion, we will define evaluable patients as those who met eligibility requirements, have initiated therapy, and were not removed from the study for non-compliance or withdrawal. Sample size recommendations for the two-stage design are determined according to Simons two-stage minimax design. The first stage will accrue a total of 16 patients (including those who were treated at the MTD in the phase I portion), if 6 or fewer of the first 16 evaluable patients do not experience a 30% decline in PSA, the study will be terminated and declared to have a negative result. If 7 or more patients out of the first 16 evaluable patients experience a 30% decline in PSA, 9 more patients will be accrued in Stage 2 (total sample size of 27). The new regimen will be declared to have activity and be worthy of further testing if 13 or more patients experience a 30% PSA decline among the 27 patients who are part of the phase II trial.

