12.2. Phase II Study Design/Endpoints

We will enroll up to 27 subjects into the Phase II portion (including the 3-6 used for establishing the MTD). We will define evaluable patients as patients who met eligibility requirements, have initiated therapy, and were not removed from the study for non-compliance or patient withdrawal.

Sample size recommendations for the two-stage design are determined according to Simon's two-stage minimax design. We project a 30% PSA decline proportion of 35%, below which the regimen will be unacceptable and a 30% PSA decline proportion of 60%, above which the regimen will be considered worthy of further exploration. The null hypothesis that the 30% PSA decline proportion is less than or equal to 35% will be tested against the alternative hypothesis that the 30% PSA decline proportion is greater than or equal to 60%.

The sample size computations were performed assuming a 0.10 one-sided level of significance and 90% power assuming a historical control value for PSA decline of 35% and the alternative

hypothesis of 60%. If 6 or fewer of the first 16 evaluable patients do not experience a 30% decline in PSA (stage 1), the study will be terminated and declared to have a negative result. If 7 or more patients out of the first 16 evaluable patients experience a 30% decline in PSA, ongoing accrual will proceed to the target sample size of 27 patients (stage 2). The new regimen will be declared active in this patient population and worthy of further testing if 13 or more patients experience a 30% PSA decline among the 27 patients entered. This two-stage design yields a 0.90 probability of a positive result if the true 30% PSA decline proportion is 60%. It yields a 0.90 probability of a negative result if the true 30% PSA decline proportion is 35%. An exact 95% binomial confidence interval will be constructed for the proportion of patients with PSA decline.

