12.5.2 Analysis of Secondary Endpoints

For PSA response, CTC response and imaging response, descriptive analysis will be done. For imaging response RECIST (Version 1.1) criteria with PCWG3 modifications will be applied. Biomarker and patient reported outcome data will be analyzed within this study as well as across additional radiolabeled-PSMA studies.

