12.6 Interim Analysis

No interim analysis is planned for the phase I portion (though safety analyses will occur in real-time and prior to each dose-escalation). For the phase II portion, accrual will be suspended

after 16 patients have been enrolled in stage 1. If at least 7 patients out of the 16 patients experienced a PSA decline > 30%, 9 more patients will be accrued as part of stage 2.

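### Section 12.6.2 sets a completer-only rule for response that conflicts with the Phase II evaluable set in 4.3 and 12.2; applied to PSA decline, it could overstate the reported rate and its CI

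*Combined protocol and SAP*

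**What the plan says.** Section 4.3 sets the Phase II population: "For the phase II portion, we will define evaluable patients as those who met eligibility requirements, have initiated therapy", with removal for non-compliance or withdrawal as the only further exclusion. Section 12.2 repeats it as "patients who met eligibility requirements, have initiated therapy, and were not removed from the study for non-compliance or patient withdrawal". Both sections apply the word evaluable to the 16-patient look.

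The final rule uses other words for its denominator: "13 or more patients experience a 30% PSA decline among the 27 patients entered" in 12.2 and "13 or more patients experience a 30% PSA decline among the 27 patients who are part of the phase II trial" in 4.3. Section 12.2 closes with the estimate: "An exact 95% binomial confidence interval will be constructed for the proportion of patients with PSA decline". That sentence names no analysis set.

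The interim paragraph in 12.6 suspends accrual "after 16 patients have been enrolled in stage 1", so it counts enrolled rather than evaluable patients.

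Section 12.6.2 sits under Reporting and Exclusions and is headed Evaluation of response. It treats as evaluable those who completed the combination ("2 doses of each investigational agent) and at least 12 weeks of subsequent follow-up evaluations"). It names no phase or endpoint and does not refer to 4.3 or 12.2. Its last sentence allows that patients not evaluable through week 12 might not be replaced. No other replacement rule was found.

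The plan uses the word response for PSA decline in the heading of 10.2 and again in 12.5.2: "For PSA response, CTC response and imaging response, descriptive analysis will be done".

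**The concern.** The two definitions treat the same patient differently. Someone who stops after the first dose because of toxicity or progression is evaluable under 12.2 and not under 12.6.2. Early progression is a ground for removal in 6.4, and some persistent blood-count toxicities before the second dose lead to permanent discontinuation in 6.2.10, so both kinds of patient are foreseeable.

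Because 12.6.2 speaks of response without limit, and PSA decline is called a response elsewhere, an analyst could apply it to the Phase II primary endpoint. In a single-arm trial of at most 27 patients, the PSA proportion and its interval are the main Phase II efficacy result. Removing patients for what happened to them after treatment began shifts that proportion upwards if they respond less often than completers. That is likely for early progressors and unknown for patients who stop for toxicity.

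**Working it through.** **Inputs from the plan (12.2).** Null proportion 0.35, alternative 0.60, one-sided level 0.10, power 0.90. Continue with at least 7 responders in 16; declare activity with at least 13 in 27.

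**Assumptions, not in the plan.** The share d of treated patients excluded by 12.6.2 is taken as 10-20%. The response rate q among those patients is varied. The plan gives neither figure.

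**1. The plan's own figures.** P(positive) = sum over x = 7 to 16 of Bin(x; 16, p) × P(Bin(11, p) ≥ 13 − x).
- p = 0.35: 0.0979
- p = 0.60: 0.9001

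The stated 0.10 and 0.90 reproduce, so the sample size is not in question.

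**2. Effect on the reported rate, by example.** Drop three non-responders and use Clopper-Pearson 95% intervals:

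| Responders | 12.2 set (27) | Completer set (24) |
|---|---|---|
| 12 | 44.4% (25.5-64.7) | 50.0% (29.1-70.9) |
| 14 | 51.9% (32.0-71.3) | 58.3% (36.6-77.9) |

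The estimate rises by 5.6 and 6.4 percentage points. With 14 responders only the completer interval excludes 35%. The go/no-go result is the same under both denominators: 12 misses the bar of 13 and 14 clears it.

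**3. Expected size of the bias.** If the true rate in all treated patients is 0.35, the completer rate is (0.35 − d·q)/(1 − d).

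| d | q = 0 | q = 0.175 | q = 0.35 |
|---|---|---|---|
| 10% | 0.389 | 0.369 | 0.350 |
| 15% | 0.412 | 0.381 | 0.350 |
| 20% | 0.438 | 0.394 | 0.350 |

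The bias therefore runs from nothing to about 9 percentage points. It depends entirely on two unknowns.

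**4. Effect on the false-positive rate within the cap.** With at most 27 patients treated, the counted responders cannot exceed all responders among the 27. Passing needs 13 counted responders, so whichever patients are excluded the probability is at most P(Bin(27, 0.35) ≥ 13) = 0.111, against 0.098 by design.

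**5. The opposite risk.** If excluded patients respond at half the overall rate and are not counted or replaced beyond 27, the false-positive rate falls to 0.074-0.052 and power at 60% falls from 0.90 to 0.86-0.79, for d of 10-20%.

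**The case against.** The strongest reply is that the plan has already named the Phase II set. Sections 4.3 and 12.2 define it for that phase, and 12.2 also contains the hypotheses, the count rule and the confidence-interval sentence. A specific definition beside the analysis should prevail over a later general paragraph. Section 12.6.2 also appeals to PCWG3, which the plan attaches to eligibility, radiographic response and progression-free survival, not to the 30% PSA decline. This stands: 12.2 is the better reading, and the plan cannot be said to prescribe a completer analysis of the primary endpoint. It does not remove the conflict, because 12.6.2 is unrestricted and the interval sentence names no set.

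Three stronger readings are tempting, and the documents do not support them.

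- *Every excluded progressor is a non-responder under 10.2.* That section bars progression only over the period of the response. PSA is drawn on Days 1, 15 and 29, so a decline seen on Day 15 and confirmed on Day 29 qualifies even if progression follows on Day 57. The q = 0 column is an extreme case, not a consequence of 10.2.
- *The 12 weeks run from the second dose.* That would end on Day 15 + 84 = Day 99, beyond the Day 85 scan, which falls (85 − 15)/7 = 10 weeks after dose 2. Patients progressing at the main scan could then be lost. But 12.6.2 refers to the Section 6.1 schedule and ends by speaking of week 12 on study, and the Protocol Summary puts the repeat imaging at 12 weeks. The wording is loose, but Day 85 is what it most plausibly means.
- *The false-positive rate could reach 0.14-0.36.* That needs replacement until 27 completers are reached, or 27/(1 − d) = about 30 to 34 patients for d of 10-20%, which exceeds the stated cap.

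It is also fair that a 95% interval excluding 35% has no role in the plan's decision, which is a count rule at one-sided 0.10.

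**Conclusion.** The point holds as a conflict of definitions with no stated scope. The exposure is the reported PSA proportion and its interval: about 6 percentage points in the three-patient illustration, and 0 to about 9 points in expectation at a true 35%, on assumed exclusions of 10-20%. The direction is upwards only if the excluded patients respond less often than completers. The go/no-go decision is little affected on the false-positive side (ceiling 0.111 against 0.098), and neither worked example changes it. If some excluded patients are responders, the completer rule would cost power instead. A reader might infer that the trial will analyse completers only, or that its type I error is seriously inflated; the text supports neither. The change should be made because it is cheap and protects the main Phase II result from a choice of denominator after the data are seen.

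**What to change.** 1. In 12.6.2, state that the completer rule does not define the Phase II PSA endpoint and is used only for a labelled sensitivity analysis. State that its 12 weeks are counted to the Day 85 efficacy visit, that is, week 12 on study.
2. In 12.2, matched in 4.3 and in the interim paragraph of 12.6, name the 12.2 evaluable set as the one used for the 16-patient look, the 27-patient rule and the exact interval.
3. State that patients in that set who stop early for toxicity or progression stay in the denominator, count as non-responders unless they had a 30% or greater PSA decline as the plan defines it, and are not replaced.

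Two related matters are separate choices and not part of this change: whether the confirmation and no-progression conditions of 10.2 apply to the primary endpoint, and whether patients removed for withdrawal or non-compliance should also count as non-responders. Either would alter the endpoint or the denominator and needs its own decision.

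The cost is wording in four places. No new data or patients are needed. The reported rate may be somewhat lower than a completer analysis would give.

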13. ADVERSE EVENT REPORTING REQUIREMENTS

Adverse event (AE) monitoring and reporting is a routine part of every clinical trial. The investigator will be required to provide appropriate information concerning any findings that suggest significant hazards, contraindications, side effects, or precautions pertinent to the safe use of the drug or device under investigation. Safety will be monitored by evaluation of adverse events reported by patients or observed by investigators or research staff, as well as by other investigations such as clinical laboratory tests, x-rays, electrocardiographs, etc.

13.1 Adverse Event Definition

An adverse event (also referred to as an adverse experience) can be any unfavorable and unintended sign (e.g., an abnormal laboratory finding), symptom, or disease temporally associated with the use of a drug, and does not imply any judgment about causality. An adverse event can arise with any use of the drug (e.g., off-label use, use in combination with another drug) and with any route of administration, formulation, or dose, including an overdose.

13.1.1. Investigational Agent Risks

There are no known contraindications for ^{177}Lu -J591, ^{177}Lu -PSMA-617 or ^{68}Ga -PSMA-HBED-CC. Because of the potential for infusion or allergic reaction, the subject should be monitored for safety for one to two hours following the infusion.

Based on prior studies, the known side effects, risks, and hazards associated with the administration of ^{177}Lu -J591, ^{177}Lu -PSMA-617 or ^{68}Ga -PSMA-HBED-CC include: infusion reaction (fever, chills, rash, hypotension, and/or hypertension after injection), xerostomia, renal insufficiency, hematological/bone marrow toxicity (thrombocytopenia, neutropenia) and transient hepatic enzyme elevations. In addition, allergic reactions including anaphylaxis, hypotension, hypertension, difficulty breathing, rash, human anti-humanized antibody (HAHA) response and CNS toxicity are a rare possibility.

Precautions/monitoring:

The infusion of ^{177}Lu -J591, ^{177}Lu -PSMA-617 or ^{68}Ga -PSMA-HBED-CC and subsequent monitoring will occur in a facility that is equipped for cardio-pulmonary resuscitation. The dispensed dose will be infused under the supervision of nuclear medicine physician or designee under the supervision of a nuclear medicine physician. Infusion-related reactions (fever, rigors) will be treated with acetaminophen, meperidine and diphenhydramine hydrochloride as clinically appropriate. Vital signs will be monitored before/after the ^{177}Lu -J591 + ^{177}Lu -PSMA-617 or ^{68}Ga -PSMA-HBED-CC infusion. Systolic and diastolic blood pressure (mm Hg), temperature, pulse rate (beats/minute), and respiratory rate (breaths/minute), will be recorded with the patient in sitting position. Any clinically significant change in the vital signs will be recorded as AEs. Serial vital signs including temperature, BP, and heart rate will be monitored within 30 minutes of the infusion, and within 30 minutes and 60 minutes (+/- 10) after the infusion (also, 90 +/- 10 minutes and 120 +/- 10 minutes for ^{177}Lu -J591 + ^{177}Lu -PSMA-617). If any subject has any adverse reaction at 60 minutes for ^{68}Ga -PSMA-HBED-CC and 120 minutes for ^{177}Lu -J591 + ^{177}Lu -PSMA-617, they will stay longer until it is resolved.

13.1.2. Adverse Event Characteristics and Related Attributions

CTCAE term (AE description) and grade: The descriptions and grading scales found in the revised NCI Common Terminology Criteria for Adverse Events (CTCAE) version 4.0 will be utilized for AE reporting. A copy of the CTCAE version 4.0 can be downloaded from the CTEP web site (<http://ctep.cancer.gov>).

Attribution of the AE:

Definite – The AE *is clearly related* to the study treatment. A reaction that follows a plausible temporal sequence from administration of the study drug and follows a known response pattern to the suspected study drug. The reaction can be confirmed with a positive re-challenge test or supporting laboratory data.

Probable – The AE *is likely related* to the study treatment. A reaction that follows a plausible temporal sequence from administration of the study drug and follows a known response pattern to the suspected study drug. The reaction cannot be reasonably explained by the known characteristics of the patient’s clinical state or other modes of therapy administered to the patient.

Possible – The AE *may be related* to the study treatment. A reaction that follows a plausible temporal sequence from administration of the study drug and follows a known response pattern to the suspected study drug. The reaction might have been produced by the patient’s clinical state or other modes of therapy administered to the patient.

Unlikely – The AE *is doubtfully related* to the study treatment. The current state of knowledge indicates that a relationship is unlikely.

Unrelated – The AE *is clearly NOT related* to the study treatment. No relationship between the experience and the administration of study drug; related to other etiologies such as concomitant medications or patient’s clinical state.

13.1.3. Recording of Adverse Events

All adverse events will be recorded on a patient specific AE log. The AE log will be maintained by the research staff and kept in the patient’s research chart.

13.1.4. Reporting of AE to WCM IRB

All AEs occurring on this study will be reported to the IRB according to the IRB policy, which can be accessed via the following link:

http://researchintegrity.weill.cornell.edu/forms_and_policies/forms/Immediate_Reporting_Policy.pdf

13.2. Definition of SAE

SAE’s include death, life threatening adverse experiences, hospitalization or prolongation of hospitalization, disability or incapacitation, overdose, congenital anomalies and any other serious events that may jeopardize the subject or require medical or surgical intervention to prevent one of the outcomes listed in this definition.

13.2.1. Reporting of SAE to IRB

All SAEs occurring on this study will be reported to the IRB according to the IRB policy, which can be accessed via the following link:

http://researchintegrity.weill.cornell.edu/forms_and_policies/forms/Immediate_Reporting_Policy.pdf

13.2.2. Reporting of SAE to FDA

If an SAE occurs on this study, the event will be filed on a MedWatch form with the FDA. The investigator must notify the FDA of any SAE's as soon as possible but no later than 7 calendar days after the initial receipt of the information

Food and Drug Administration
Center for Drug Evaluation and Research
Central Document Room
[name]
[name]

13.3. AE/SAE Follow Up

All SAEs and AEs reported during this study will be followed until resolution or until the investigator confirms that the AE/SAE has stabilized and no more follow-up is required. This requirement indicates that follow-up may be required for some events after the patient discontinues participation from the study.

14. DATA AND SAFETY MONITORING PLAN (DSMP)

This study will utilize the Weill Cornell Medicine (WCM) Institutional Data Safety Monitoring Board (DSMB) and follow its policies and procedures for monitoring this study for safety concerns, with ongoing updates from the Study Chair on a continuous basis.

The Weill Cornell's DSMB is comprised of medical specialists and advisors on human rights issues in human subjects research. The DSMB currently has 9 members, meets at quarterly intervals during the year, and carries out ongoing review of protocols submitted throughout the year. Once a protocol has been submitted and approved by the Institutional Review Board (IRB) and is recommended for oversight by the DSMB, the Board determines if the protocol will be reviewed quarterly, semi-annually, or annually.

The DSMB evaluates the accumulated data from the study in order to monitor the safety of subjects throughout the trial and reviews the risks and benefits, as well as the efficacy, of the study. The DSMB will also evaluate the overall trial conduct and progress. Ultimately, the DSMB validates the continuation of the trial or determines if a study needs modification or termination.

Reports to the DSMB will include the following items for review:

- Completed DSMB Periodic Review Form.
- Synopsis of the study to date.
- IRB approved consent form.
- IRB current protocol.
- Summary table of study results.
- Adverse event table.
- Data safety monitoring plan.

Safety monitoring is carried out to ensure and maintain the scientific integrity of human subject research projects and to protect the safety of human subjects. Safety monitoring can be viewed as any process during a clinical trial that involves the review of accumulated outcome data for groups of patient–subjects to determine if any of the treatment procedures practiced should be altered or stopped. NIH Guidelines (1998, 2000) specify that all clinical trials should have a system in place for appropriate oversight and monitoring to ensure the safety of participants and the validity of the data.

Monitoring activities will be commensurate with the nature, size, and complexity of the trial in accordance with institutional policies and will be determined after IRB and DSMB review of the protocol immediately prior to study activation. For a small, single–center study, usually a statistician in conjunction with a Safety Officer performs the monitoring. For that single–site, high–risk trials, a DSMB may be appropriate. For larger, single or multi–site studies, a committee, often called a Data Safety Monitoring Board (DSMB), usually performs the monitoring. Ongoing review of the data by an independent individual or committee assures the investigators, the IRB, the study’s sponsor, and the funding agency that the trial can continue without jeopardizing subjects’ safety.

Weill Cornell Medicine requires that all research approved by the WCMC IRB include an appropriate plan for the monitoring of data to ensure the safety of human subjects. Research supported by Federal agencies will be monitored according to all regulations and guidelines of the relevant Federal agency.

For this study, the DSMB will be notified after each cohort has been completed prior to dose escalation to the next cohort and prior to transition from phase I to phase II. In addition, a report will be made to the DSMB every 6 months.

14.1 Medical Monitor

The medical monitor is required to review all unanticipated problems involving risk to subjects or others, serious adverse events and all subject deaths associated with the protocol and provide an unbiased written report of the event. At a minimum, the medical monitor must comment on the outcomes of the event or problem and in case of a serious adverse event or death, comment on the relationship to participation in the study. The medical monitor must also indicate whether he/she concurs with the details of the report provided by the principal investigator. Reports for events

determined by either the investigator or medical monitor to be possibly or definitely related to participation and reports of events resulting in death must be promptly forwarded to the appropriate committees/agencies. This individual will be a qualified physician, other than the principal Investigator, not associated with this particular study, able to provide medical care to research subjects for conditions that may arise during the conduct of this study, and will monitor the subjects during the conduct of the study.

[name] will serve as the Medical Monitor for this study.

